8.9.3. Safety Telephone Calls

A safety telephone call is a telephone call made to the participant by trained site personnel. This call will follow a script, which will facilitate the collection of relevant safety information. Safety telephone calls will follow a schedule for each participant, as shown in the SoE ([Table 1](#)). The participant will be interviewed according to the script about occurrence of AEs, MAAEs, SAEs, AESIs, AEs leading to withdrawal from study participation, concomitant medications associated with those events, and any nonstudy vaccinations. All safety information collected from the telephone contact must be documented in source documents as described by the participant and not documented on the script used for the safety telephone contact. An unscheduled follow up safety call may be triggered if an eDiary record results in identification of a relevant safety event.

8.9.4. Use of Electronic Diaries

At the time of consent, the participants must confirm they will be willing to complete an eDiary (for 7-day reactogenicity). The local and systemic ARs that will be solicited by the eDiary are described in [Table 5](#).

Solicited local and systemic reactogenicity ARs will be collected on the day of study intervention and during the 7 days after study intervention (ie, the day of dosing and 6 subsequent days). Details on the recording of local and systemic ARs are included in [Section 8.10.3](#).

At the dosing visit, participants will record data into the eDiary starting approximately 30 minutes after dosing under supervision of the site staff to ensure successful entry of assessments. The 30-minute observation period is an opportunity for site staff to train the participant on eDiary completion requirements. The site staff will perform any retraining as necessary throughout the study.

At the dosing visit, participants will be instructed on thermometer usage to measure body temperature, ruler usage to measure injection site erythema (redness) and swelling/induration (hardness), and self-assessment for localized axillary (underarm) swelling or tenderness ipsilateral (on the same side as the injection arm[s]) during the 7 days after study injection. Daily

oral temperature measurement should be performed at approximately the same time each day using the thermometer provided by the site staff.

The participant will be trained on how to complete the eDiary questions according to the SoE (Table 1) and also reminded to call the site immediately if they experience any condition. If eDiary questions result in identification of relevant safety events according to the study period or symptoms of ILI, a follow-up call will be triggered. The results of the call should be recorded in the appropriate source documentation.

If a participant does not respond to the eDiary questions according to the SoE, site staff will follow-up with the participant.

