8.16.1.1. EFS

At Day 1, the EFS will be collected by clinical staff for participants aged 65 years and older. This scale is a brief, valid, and reliable tool for assessment of frailty across 9 domains: cognition, general health status, functional independence, social support, medication use, nutrition, mood, continence, and functional performance.

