9.4. Analyses Populations

Table 6: Populations for Analyses

Analysis Sets	Description
Randomization Set	All participants who are randomized, regardless of the participants' treatment status in the study.
Full Analysis Set (FAS)	All randomized participants who received any study intervention. Participants will be analyzed according to the group to which they were randomized.
Modified Intent-to-Treat Set (mITT)	All participants in the FAS except those who discontinued from the study prior to 14 days following administration of study intervention. The mITT Set will be used as the primary analysis set for efficacy endpoints evaluating superiority. Participants will be analyzed according to the group to which they were randomized.
Per-Protocol (PP) Set	All participants in the mITT, excluding those with significant protocol deviations that could adversely impact efficacy (eg, disease or

Analysis Sets	Description
	
therapeutic intervention that might cause suboptimal response to the study intervention). The PP Set will be used as the primary analysis set for efficacy endpoints evaluating noninferiority.
 
Participants will be analyzed according to the group to which they were randomized.

Immunogenicity Subset	
All participants in the biomarker subset who are in the FAS and have baseline and Day 29 antibody assessment via HAI assay.
 
Participants will be analyzed according to the group to which they were randomized.

PP Immunogenicity Subset	
The PP Immunogenicity Subset includes all participants in the Immunogenicity Subset who received the planned dose of IP, complied with the immunogenicity testing schedule, and had no major protocol deviations that impact the immunogenicity assessment. Participants with RT-PCR–confirmed influenza between Days 1 to 29 will be removed from the PP Immunogenicity Set.
 
The PP Immunogenicity Set will be used for all analyses of immunogenicity unless specified otherwise.
 
Participants will be analyzed according to the group to which they were randomized.

Solicited Safety Set	
The Solicited Safety Set consists of all randomized participants who received any study intervention and contributed to any solicited adverse reaction (AR) data.
 
The Solicited Safety Set will be used for the analyses of solicited ARs and participants will be included in the vaccination group corresponding to the study intervention that they actually received.

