5.5. Solicited Safety Set

The Solicited Safety Set consists of all randomized participants who received any study intervention and contributed to any solicited AR data.

The Solicited Safety Set will be used for the analyses of solicited ARs and participants will be included in the vaccination group corresponding to the study intervention that they actually received.

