6.1.3. Data Precision

For the summary statistics of numeric variables, unless otherwise specified, the display precision will follow the programming standards presented in [Appendix B](#).

When count data are presented, the percentage will be suppressed when the count is zero in order to draw attention to the non-zero counts. If the count equals the denominator, the percentage will be displayed as 100.

A row denoted “Missing” will be included in count tabulations where specified on the mock shells to account for dropouts and missing values. The denominator for all percentages will be the number of participants in the vaccination group within the analysis set of interest, unless otherwise specified.

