6.1.5. Handling Missing and Incomplete Data

- Imputation rules for missing dates of prior/concomitant medications, non-study vaccinations, and procedures are provided in [Appendix C](#).
- Imputation rules for missing AE dates are provided in [Appendix D](#).
- If the laboratory results are reported as below the lower limit of quantification (LLOQ) (e.g. < 0.1), the numeric values will be replaced by $0.5 \times \text{LLOQ}$ in the summary when treating the results as continuous variables. If the laboratory results are reported as greater than the upper limit of quantification (ULOQ) (e.g. > 3000), the numeric values will be replaced by the ULOQ when computing summary statistics for continuous variables.
- Other incomplete/missing data will not be imputed, unless specified otherwise.

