6.2.2. Demographics and Baseline Characteristics

Descriptive statistics will be calculated for the following continuous demographic and baseline characteristics: age (years), weight (kg), height (cm), and body mass index (BMI) (kg/m^2).

The number and percentage of participants will be provided for categorical variables:

- Age group 1 (age strata at randomization: ≥ 50 to < 65 years, or ≥ 65 years) per eCRF
- Age group 2 (≥ 50 to < 65 years, ≥ 65 to < 75 years, or ≥ 75 years) per eCRF
- Sex (Male, Female)
- Race (White, Black or African American, Asian, American Indian or Alaska Native, Native Hawaiian or Other Pacific Islander, Other, Not Reported, Unknown)
- Ethnicity (Hispanic or Latino, Not Hispanic or Latino, Not Reported, Unknown)
- Influenza vaccine status in the previous flu season (received previous season influenza vaccine or did not receive previous season influenza vaccine) per eCRF
- EFS total score category (Fit: 0-3, Vulnerable: 4-5, - Frail: 6 or more)

The summaries will be provided separately based on the Randomization Set, Safety Set, mITT Set, and PP Set.

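### The 30-minute clinic entry alone can admit a participant to the 7-day reactogenicity denominator as reaction-free, and the same default denominator dilutes the baseline frailty percentages

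*Protocol*

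**What the plan says.** **Set membership.** SAP 5.5 reads: "The Solicited Safety Set consists of all randomized participants who received any study intervention and contributed to any solicited AR data". Protocol 9.4, Table 6, has the same rule: "received any study intervention and contributed to any solicited adverse reaction (AR) data". Neither asks for a minimum number of diary days.

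**First entry.** Protocol 8.9.4 has participants start the eDiary in clinic, approximately "30 minutes after dosing under supervision of the site staff to ensure successful entry of assessments". Footnote 13 of the Schedule of Events repeats this.

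**Denominator and missing data.** SAP 6.1.3: "The denominator for all percentages will be the number of participants in the vaccination group within the analysis set of interest, unless otherwise specified". A row for missing values "will be included in count tabulations where specified on the mock shells to account for dropouts and missing values". SAP 6.1.5: "Other incomplete/missing data will not be imputed, unless specified otherwise". SAP 6.7.1, which specifies the 7-day percentages and the Clopper-Pearson intervals, names no other denominator.

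**Other sources of reactions.** The schedule has a Day 8 contact with review of the solicited-reaction diary. Protocol 8.9.4 has sites follow up diary non-response. Protocol 8.10.3 has staff record unentered reactions on the Reactogenicity eCRF page, and SAP 6.7.1 counts eCRF reactions in the analysis.

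**Frailty.** Protocol 8.16.1.1: "At Day 1, the EFS will be collected by clinical staff for participants aged 65 years and older". SAP 6.2.2 lists among the baseline variables "EFS total score category (Fit: 0-3, Vulnerable: 4-5, - Frail: 6 or more" and tabulates them on the Randomization, Safety, mITT and PP Sets, which include ages 50 to 64.

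**The concern.** The requirement to have contributed solicited data should separate the Solicited Safety Set from the Safety Set. Because the supervised clinic entry meets it, the set is close to everyone dosed, including people about whom nothing is known after they left the clinic. An observation at 30 minutes cannot stand for a week: Protocol 2.3.2 says that local reactions to the sponsor's related vaccines usually appeared within 24 hours. Anyone unobserved after the clinic and with no reaction on record adds to the denominator and not to the numerator.

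Solicited reactions through 7 days are a primary safety endpoint. The bias is downward, which favours the product. With about 11,500 per arm, the exact interval is narrow enough that a modest loss of follow-up can move the estimate by more than the interval allows.

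The frailty table has the same default denominator but a different cause: people aged 50 to 64 are never assessed, yet they are counted in the denominator.

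**Working it through.** The documents state no reactogenicity rate, diary-completion rate or frailty percentage, so there is no planned figure to reproduce. Group size is about 11,500 per arm (SAP 4.3). The share aged 65 and over is at least 50% (SAP 4.4). All other inputs below are assumptions.

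**Solicited reactions.** Let p be the true 7-day rate, m the share with only the clinic entry, and c the share of their reactions recovered (noted at 30 minutes, at the Day 8 contact, on non-response follow-up, or on the eCRF). Assume that non-completers react at the same rate as completers. Then

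reported rate = p × (1 − m(1 − c)).

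For p = 70% and m = 5%: with c = 0, 70 × 0.95 = 66.5%; with c = 0.5, 70 × 0.975 = 68.25%.

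Reported rate, with the Clopper-Pearson 95% CI at N = 11,500:

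| p | m | c = 0 | c = 0.5 |
|---|---|---|---|
| 70% | 2% | 68.6% (67.7 to 69.4) | 69.3% (68.4 to 70.1) |
| 70% | 5% | 66.5% (65.6 to 67.4) | 68.25% (67.4 to 69.1) |
| 70% | 10% | 63.0% (62.1 to 63.9) | 66.5% (65.6 to 67.4) |
| 30% | 5% | 28.5% (27.7 to 29.3) | 29.25% (28.4 to 30.1) |
| 30% | 10% | 27.0% (26.2 to 27.8) | 28.5% (27.7 to 29.3) |

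The normal half-width at 70% is 1.96 × √(0.7 × 0.3 / 11,500) = 0.84 points. The bias, 70 × m(1 − c) points, exceeds it once m passes 0.84/70 = 1.2% with no recovery, or 0.84/35 = 2.4% with half recovered. Two cells of the table, both with half recovery, still cover the true rate: p = 70% with m = 2%, and p = 30% with m = 5%.

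With m and c equal in both arms, the between-arm difference shrinks by the same factor. A true 70% against 50%, a gap of 20 points, becomes 19 at m = 5% with c = 0 and 19.5 with c = 0.5. The ratio between arms is unchanged.

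**Frailty.** Tabulated percentage = percentage among those aged 65 and over × share aged 65 and over. For an assumed 20% frail: 20 × 0.5 = 10% at the minimum share, 20 × 0.6 = 12% at a 60% share, and 20 × 0.7 = 14% at a 70% share.

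**The case against.** The strongest answer is that the diary is not the only source. Every participant has a Day 8 contact, sites chase non-response, and reactions entered on the eCRF count. This stands against the tempting reading that anyone without a home diary is scored as reaction-free: only those with no reaction reported by any route are. These safeguards can add to the numerator, but they do not take an unobserved person out of the denominator.

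Second, SAP 6.1.5 leaves missing data unimputed, and treating a blank diary as no reaction would amount to imputation. SAP 6.1.3 also yields where something else is specified and allows a row for missing values. The mock shells are not in the documents, so the final layout cannot be judged. However, no imputation step is needed for the dilution: counting reactors over the whole set produces it. A row for missing values would show the gap without changing the divisor. Where the SAP wants another denominator its text says so, as for screen-failure reasons in SAP 6.2.1. SAP 6.2.2 and 6.7.1 do not.

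Third, solicited reactions are summarised descriptively, with no test or margin, so no formal inference changes. That is correct and limits the weight of the point.

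On frailty, the baseline table also gives age-group counts, so a reader could recover the percentage among those aged 65 and over. The exploratory frailty objective is already confined to that age group and belongs to a separate plan (SAP 2.3).

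**Conclusion.** The point holds in a limited form. On the written rules, a participant with only the clinic entry and no reaction reported by any route is counted as reaction-free for 7 days, and the 7-day rates are biased low to that extent. The size cannot be derived from the documents. At an assumed true rate of 70% and m = 5%, the loss is 3.5 points with no recovery and 1.75 points with half recovered, against a half-width of about 0.84 points. If m is about 1%, or recovery is high, the loss is within sampling error. All of this assumes that non-completers react at the same rate as completers.

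A reader might also infer that the frailty percentages are halved. That is true only if exactly half of the participants are 65 or over. The planned 50% is a minimum, and the factor is whatever share is enrolled. Only the baseline table is affected.

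**What to change.** (a) In SAP 6.7.1, report by arm the number of participants with solicited reaction data after the clinic entry, by diary day, together with the number who had a documented Day 8 assessment of presence or absence of reactions. Give the 7-day percentages and exact CIs among the participants with such data, alongside the full-set table. The full-set table should stay, because restricting to post-clinic data alone would drop reactions seen only at 30 minutes or recorded only on the eCRF. The by-day counts are needed because a single entry on the evening of Day 1 is not 7 days of follow-up.

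(b) In SAP 6.2.2, compute the frailty category percentages among participants aged 65 and over in each analysis set, with a row for those aged 65 and over without a score.

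The cost is a few sentences of SAP text, one extra table and a changed denominator in the baseline program; data collection is unchanged. In the added table the reaction rates will be slightly higher, hence less favourable, on a slightly smaller N.

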8.9.5. Recording and Follow-up of Pregnancy

The effects of mRNA-1010 on the unborn child and on the newborn baby are not known. Because of this, it is important that study participants are not pregnant and do not become pregnant during the course of the study. Female individuals who have a positive pregnancy test at the Screening visit should not be enrolled; participants who have a positive pregnancy test at Day 1 must not receive the study intervention and should be withdrawn from the study. Female participants who become pregnant at any time during the study after receiving the study intervention should be asked to remain in the study and be followed-up for safety. Pregnancy testing is scheduled to occur at the Screening visit and Day 1 (Table 1). Additional pregnancy testing during the study may also be performed if required by local regulatory requirements.

Pregnancies reported in female participants will be collected after the start of study intervention and until Day 361 (Month 12)/EoS.

- If a pregnancy is reported, the Investigator should inform the Sponsor within 24 hours of learning of the pregnancy and should follow the procedures outlined in this section.
- Abnormal pregnancy outcomes (eg, spontaneous abortion, fetal death, stillbirth, congenital anomalies, ectopic pregnancy) are considered SAEs.

Pregnancies occurring in participants after administration of study intervention must be reported to the Sponsor or designee within 24 hours of the site learning of its occurrence. If the participant agrees to submit this information, the pregnancy must be followed to determine the outcome, including spontaneous or voluntary termination, details of the birth, and the presence or absence of any birth defects, congenital abnormalities, or maternal and/or newborn complications. This follow-up should occur even if intended duration of the safety follow-up for the study has ended. Pregnancy report forms will be distributed to the study site to be used for this purpose. The Investigator must immediately (within 24 hours of awareness) report to the Sponsor any pregnancy resulting in an abnormal outcome according to the procedures described for SAEs.

8.9.6. Recording and Follow-up of an AE and/or SAE

The Investigator is responsible for ensuring that all AEs and SAEs are recorded in the eCRF and reported to the Sponsor.

Solicited ARs will be collected from Day 1 through 7 days after the study intervention (ie, the day of injection and 6 subsequent days). Other (unsolicited) AEs will be collected from Day 1 through 28 days after the study intervention (ie, the day of injection and 27 subsequent days).

MAAEs, SAEs, and AESIs will be collected from participants as specified in the SoE (Table 1) from Day 1 until the end of their participation in the study.

At every clinic visit or telephone contact, participants will be asked a standard question to elicit any medically related changes in their well-being (including surveillance for respiratory viral infection symptoms) according to the scripts provided. Participants will also be asked if they have been hospitalized, had any accidents, used any new medications, changed concomitant medication regimens (both prescription and over-the-counter medications), or had any non-study vaccinations.

In addition to participant observations, physical examination findings and other documents relevant to participant safety classified as an AE will be documented on the AE page of the eCRF.

After the initial AE/SAE report, the Investigator is required to proactively follow each participant at subsequent visits/contacts. All AEs and SAEs will be treated as medically appropriate and followed until resolution, stabilization, the event is otherwise explained, or the participant is LTFU (as defined in Section 7.2).

